## RESEARCH DESIGN AND METHODS

Previous Research: With funding from the Greater Wisconsin Agency on Aging Resources, research was conducted to develop an intervention to reduce sedentary behavior and examine the feasibility of implementing the intervention by a State Aging Unit in a community setting. The research was conducted in two communities in Rock County, Wisconsin which is made up of

small urban and rural communities. The older adults in these communities had high levels of sedentary behavior (averaging almost 11 hours of their waking hours per day sitting) and their function scores were below the population average. A 4-week intervention based on self-regulation theory and designed to break up extended sitting time by standing up multiple times during the day significantly ( $p < 0.05$ ) reduced sedentary behavior (60 min/day), was associated with moderate increases in light intensity physical activity (effect size = 0.52; 35 minutes/day), and large effect size improvements in mobility (i.e., gait speed; effect size = 0.74) as well as vitality (effect size = 1.15). Importantly, reductions in sedentary behavior were sustained 4 weeks after the intervention ended. Strategies used most often included standing up during television commercials, and spreading household chores out across the day. Additional strategies included getting up to get a drink of water, and setting a timer to stand up. Twenty participants (out of a total of 25) completed the 4-week program and 90% of the participants expressed high satisfaction with the program (e.g., “What a great program. It made me realize how much I sit during the day and helped me manage my sitting time”). Also, participants indicated that breaking up sitting time was more appealing to them than increasing exercise. Further, the intervention was found to be feasible for staff to implement. The director of the Rock County Council on Aging who led the workshops stated “The intervention worked because it was simple. It is not complex and that is the beauty of it.” Thus, our pilot results are quite promising and represent the development, preliminary feasibility, and piloting stages of the *Stand Up & Move More* intervention in a small sample of older adults.

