*Demographic and Health History Questionnaire*: At baseline, participants will be asked to complete a questionnaire regarding health status and demographic information (date of birth, sex, race, ethnicity, education, and marital status), current physical activity, smoking status, and current alcohol intake.

*Mediators of Behavior Change*: As suggested by NIH reviewers, we have added selected mediators of behavior change. Participants will complete questionnaires assessing self-regulation strategies, self-efficacy, and outcome expectancies.

*Adherence to the Intervention and Outcome Assessments*: Adherence to the *Stand Up and Move More* intervention workshop will consist of participants attending at least 50% of the sessions. As for outcome assessments, adherence to wearing the accelerometers will be defined as wearing the monitors 4 out of 7 days.

*Analyses*: The primary sedentary behavior outcome variables include total sedentary time, time spent sitting in long bouts (i.e.,  $\geq 60$  minutes), and sit-to-stand transitions as measured by the activPAL. These outcomes will be examined adjusting for monitor wear time if wear time differs between groups. We will also be able to analyze changes in specific domains of sedentary behavior (e.g., watching TV, reading) from data obtained from the sedentary behavior questionnaire. A 2 (groups) x 3 trials (pre, post-1, and post-2) repeated measures ANOVA will be used to examine differences between groups in changes in sedentary behavior before and following the intervention and control conditions. Similarly, for the secondary variables of physical activity, functional performance, health-related quality of life, and mediators of behavior change, a series of 2 x 3 repeated measures ANOVA's will be performed. Significant main effects and interactions will be assessed with planned contrasts. Effect sizes will be calculated to examine the magnitude of differences between groups as well as the magnitude of change from pre to post-intervention according to methods described by Cohen. In addition,

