Adverse Event and Serious Adverse Event Collection and Reporting: Adverse events are not expected to occur. The health program facilitators will, however, at the beginning of each workshop session, distribute a brief questionnaire asking about any adverse events (e.g., falling while standing up, injury, muscle soreness, and/or increases in pain) that may have occurred during the previous week. Other information to be gathered at the beginning of each session includes whether any of the participants were sick or sought healthcare during the past week. The health program facilitators will review the responses and then follow-up with respondents during the break or at the end of the session. (Note: the health program facilitators will be trained by [name] to assess adverse events as part of a day-long ‘Stand Up and Move More’ workshop training session for the community partners). Adverse events (AE) occurring during the study will be documented and reported (to the DSMB, IRB, and NIA) by the Principal Investigator (PI). The occurrence of AEs will be assessed on an ongoing basis during the intervention. If patterns of recurrent AEs across participants suggest modifications of the study protocol are required, such changes will be implemented in consultation with NIH staff and the IRB of record. The PI will be responsible for ensuring participant safety on a daily basis. The PI or research assistant will call the health program facilitators on a weekly basis during the workshop to discuss safety concerns and delivery of intervention content. In addition, bi-weekly phone calls will occur with the PI, [name], and [name] (for quality assurance). A Data and Safety Monitoring Board (DSMB) will oversee safety monitoring and will act in an advisory capacity to the NIA Director to monitor participant safety.

Protection Against Study Risks:

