## **3). Data Safety and Monitoring**

The UW-Madison will be the IRB of record and our community partners, the four directors and staff of the Aging Network who regularly offer health promotion programs to older adults in their counties, will receive human subjects training through the UW-Madison. The PI will be responsible for ensuring participants' safety on a daily basis. The DSMB will act in an advisory capacity to the NIA Director to monitor participants' safety, evaluate the progress of the study, review procedures for maintaining the confidentiality of data, and review the quality of data collection, management, and analyses.

Frequency of Data and Safety Monitoring: The data will be reviewed every 6 months throughout the duration of the study. The PI will be informed of serious AE as soon as they occur and will

notify the NIA and DSMB within 24 hours of notification. The DSMB will meet twice annually via conference call to review study progress, data quality, and participant safety.

Content of Data and Safety Monitoring Report: The content of the report will include: 1) study status, 2) demographic characteristics of enrolled participants, 3) enrollment and attrition statistics, 4) quality assurance and regulatory issues, descriptions of any AEs and/or SAEs, and 6) intervention efficacy (if applicable).

Data and Safety Monitoring Board Membership and Affiliation: The Data and Safety Monitoring Board (DSMB) is composed of three members and includes experts in or representatives of the fields of relevant clinical expertise, clinical trial methodology, and biostatistics:

1). [name]. (Chair of the DSMB)  
Professor of Internal Medicine, Gerontology & Geriatric Medicine  
Wake Forest School of Medicine  
Winston-Salem, NC 27157  
Email: [[contact]](mailto:[contact])  
[contact]

[name] is the Deputy Director of the Sticht Center on Aging at Wake Forest School of Medicine. She has a Ph.D. in exercise physiology and conducts research on the effects of exercise on various health outcomes in older adults (e.g., weight loss, weight regain, inflammation).

2). [name]., R.N.  
Associate Professor of Nursing  
Sinclair School of Nursing  
University of Missouri  
Columbia, MO 65211  
Email: [[contact]](mailto:[contact])  
[contact]

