## **DATA COLLECTION AND QUALITY ASSURANCE**

Data Collection: All study data will be collected solely for the research purposes of this study. Outcome assessments consisting of accelerometer, questionnaire and interview data, as well as the Short Physical Performance Battery (i.e., balance, gait speed & chair stands) will be assessed by research assistants from the UW-Madison who are blinded to group assignment (Note: every effort will be made to ensure the assessors remain blinded throughout the duration of the study). The research assistants including the PI ([name]) will travel to the county sites on designated days to collect data at baseline, after the 4-week intervention, and at follow-up (12 weeks). The research assistants will be trained by [name] to complete data assessments prior to data collection. Data collection forms will be standardized and the participant's ID number will be recorded on the forms (rather than their names). Source documents for each participant's data (i.e., participant binder) will be stored in a locked cabinet in [name] laboratory. Data will also be entered (using ID numbers only) by one of the research assistants into an electronic database using SPSS statistical computing environment. The data will be stored in a password protected area with firewall protection. Only designated personnel on the project will have access to the file and password.

Data Management: The UW-Madison is the lead site for this study. [name] will be responsible for data management including activities such as development and maintenance of study materials including a manual of procedures (MOP) and data collection forms; training and supervising research assistants during data collection; overseeing data management via a secure data management system; reviewing data entry for possible errors; and assisting with data analyses. The community partners will not be involved in collecting, storing or analyzing

the data. Their primary responsibilities include recruiting participants, facilitating the *Stand Up and Move More* workshops, and providing information (via a semi-structured interview) about the feasibility of implementing the workshops. The Steering Committee for this study will meet bi-weekly to discuss study progress, data management, and quality control (with additional conference calls as needed).

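### Adverse-event questioning in the intervention arm depends on attendance and a one-week recall, so absent participants are not asked and prompt notice of serious events is not assured for them

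*Combined protocol and SAP*

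**What the plan says.** The Safety section (Adverse Event and Serious Adverse Event Collection and Reporting) says that facilitators will, "at the beginning of each workshop session, distribute a brief questionnaire asking about any adverse events" "that may have occurred during the previous week". They also ask "whether any of the participants were sick or sought healthcare during the past week". They review the answers and then "follow-up with respondents during the break or at the end of the session". The PI or a research assistant telephones the facilitators weekly about safety and delivery.

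Table 2 (Schedule of Assessments) marks adverse events at Sessions 2, 3 and 4, at the 8-week refresher and at the 12-week follow-up. Protection Against Study Risks adds that participants raise problems at the weekly meetings. It also says they are told what to report, and to whom, if something happens while they are taking part in the workshop.

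On serious events, Frequency of Data and Safety Monitoring states: "The PI will be informed of serious AE as soon as they occur". The PI then has 24 hours from being notified to tell the NIA and the DSMB.

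Two other statements bear on this. Workshop adherence is defined as "participants attending at least 50% of the sessions". Data Management says of the study data: "The community partners will not be involved in collecting, storing or analyzing" them.

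**The concern.** The form looks for falls, injury, soreness, pain, sickness and use of healthcare. Several of these are plausible reasons for missing a session. If the form reaches only those in the room, whether an event is elicited depends on whether the participant was well enough to come, and the error runs towards too few events.

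The PI is to judge whether recurrent events call for a protocol change, and the DSMB is to receive descriptions of events. Both would lean on the attendees. These losses arise in weeks when a session was held, so they are distinct from the calendar gaps between sessions.

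**Working it through.** The plan states no figure on this point to reproduce. The check is a comparison of routes, followed by simple counts.

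**Routes open to a participant who is absent from a session**

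- Session form, with its sickness and healthcare questions: requires presence.
- Facilitator follow-up: limited to those who answered the form, so requires presence.
- Reports at weekly meetings: require presence, but carry no stated one-week limit.
- 12-week follow-up entry in Table 2: requires attending an assessment visit; its recall period is not described.
- Self-report: does not require presence, but the participant must start it.
- Weekly calls to facilitators: do not require presence, but pass on only what the facilitator already knows. No duty to find out why someone was absent is stated.

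No route has staff contact the absentee or the person who has stopped attending.

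**Recall.** Assume weekly sessions exactly seven days apart: Session 1 on day 0, then days 7, 14 and 21. Take a fall on day 9.

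- Session 3 attended on day 14: 14 − 9 = 5 days, inside the window.
- Session 3 missed, return on day 21: 21 − 9 = 12 days, outside the window.

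**Fewest session forms for a participant counted as adherent.** Table 2 has no adverse-event entry at Session 1.

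- 50% of the four weekly sessions: 0.5 × 4 = 2 attended. If one is Session 1, 2 − 1 = 1 of the 3 weekly forms. In recall days, that is 7 of 3 × 7 = 21.
- If the refresher counts as a session: 0.5 × 5 = 2.5, so 3 attended. If one is Session 1, 3 − 1 = 2 of the 4 session forms. In recall days, that is 14 of 4 × 7 = 28.

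Either case gains the week-12 entry if that visit is attended. In the first case the refresher adds a form if attended. The text speaks of every session, which would include Session 1, but a form there would cover only the week before the workshop began.

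**People who may stop attending.** The planned attrition of about 20% gives 0.20 × 40 = 8 intervention participants. In the pilot, "Twenty participants (out of a total of 25) completed the 4-week program", so 25 − 20 = 5 did not, and 5/25 = 20%. These figures show how many might receive no further session form. They do not count missed events: the attrition figure is a sample-size allowance, and no reasons are given for the pilot non-completers.

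**The case against.** A reader might infer that only session attendees are ever asked. Table 2 does not support that: the 12-week entry belongs to an assessment visit, and someone who has left the workshops could still attend it. It too depends on attendance, however.

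A reader might also infer that serious events cannot reach the PI promptly. That goes too far. A participant or relative may report at once, and a facilitator who knows of an injury can raise it. The 24-hour clock starting at notification is not a fault either, since nobody can report what they do not yet know. What remains is that prompt notice is not assured for absentees.

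A returning participant can mention an older event at a weekly meeting, which is why the one-week form need not, rather than cannot, capture the missed week.

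Absentee contact may be covered in the manual of procedures or the facilitators' training day, neither of which is available here. The recipient of self-reports may be on pages not shown, so I make no point of that. Still, a rule that decides who is asked about harm belongs in the protocol that the IRB and DSMB review.

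The stakes are limited. Adverse events are not an analysed outcome, the intervention is described as minimal risk, and the pilot reported no injuries and no increase in pain. The conflict over data collection may be only wording, if Data Management was meant for outcome data; it does not itself bear on absentees.

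**Conclusion.** The point holds as a weakness in how harms are ascertained. Active questioning in the intervention arm requires attendance, the one-week recall does not reliably recover a missed week, and no contact is described for those who stop attending. Notice of serious events to the PI can be prompt but is not secured for absentees.

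The size can be given only as forms: at worst 1 of 3 weekly-session forms, or 2 of 4 session forms if the refresher counts, with the week-12 entry in addition if attended. This assumes Table 2 governs when the form is given. The day counts also assume seven-day spacing and no overlap between recall windows. A reader might want a percentage of events missed, but the documents give neither event rates nor absence rates linked to events. The direction, towards too few events, rests on the judgement that the events sought make absence more likely. No efficacy conclusion is affected. The change is cheap and worth making.

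**What to change.** Amend the adverse-event section as follows:

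1. Word the form to cover the time since the participant's last report. This would also reach the weeks between Session 4, the refresher and week 12, which one-week forms leave out even with full attendance.
2. For anyone absent from a session, have the facilitator or other existing unblinded staff telephone within a fixed few days and complete the same form. The blinded research assistants who perform the assessments should not make these calls. The documents do not say who records attendance, so name that person.
3. For people who stop attending, continue the calls at the scheduled adverse-event time points.
4. Require the facilitator to tell the PI the same day about any serious event learned of, without waiting for the weekly call.
5. Reconcile Data Management, which excludes community partners from data collection, with the facilitators' role in handing out and reviewing adverse-event forms.

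The cost is a few short calls per workshop and some protocol wording. Reported event counts may rise, which should be expected when they are read against the pilot.

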*\*Note:* [name], our community research associate, will provide the training and fidelity monitoring of our community partners. She has been involved in statewide coordination of evidence-based health promotion programs for older adults in Wisconsin for over 9 years. Part of her responsibilities have included training, overseeing, and fidelity monitoring for health promotion programs (e.g., the “Chronic Disease Self-Management” program). In addition, [name] (co-investigator) has expertise in developing tools for fidelity monitoring for the health promotion program “Stepping On.” These fidelity tools are used nationally to ensure high fidelity with dissemination of falls prevention programs. Treatment fidelity implementation in the proposed study is consistent with NIH Behavior Change Consortium Treatment Fidelity Workgroup recommendations involving study design, training of providers, delivery of treatment, receipt of treatment, and enactment of treatment skills.

**Wait-List Control Group:** Older adults assigned to the control group will be instructed to go about their daily routines during the first 12 weeks of the study. They will complete, in the same manner as the intervention group, assessments at baseline, 4, and 12 weeks. The control participants will receive the *Stand Up & Move More* intervention after 12 weeks.

**Measures:** Data collection sessions will be held the week prior to beginning the intervention (at the introductory meeting), at 4 weeks (following the delivery of the intervention), and at 12 weeks (follow-up) at readily accessible sites in each county (see Appendices for a summary table of outcomes assessment). Assessments will be completed by assessors trained by [name]. The assessors will be blinded to group assignment, and every effort will be made to ensure the assessors remain blinded throughout the duration of the study.

**Sedentary behavior** will be assessed both subjectively and objectively: **(a)** Participants will be interviewed by the investigators about their time spent sitting during the day in different activities (e.g., watching TV, reading) over the past week using a previously validated questionnaire for older adults; **(b)** Activity Monitors will be worn at each assessment for one week: The *activPAL*

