## **SAFETY**

### ***Data Safety & Monitoring Plan***

#### **1). Participants Safety:**

##### Potential Risks and Benefits for Participants

*Risks:* Participants will be asked to think of things they can do safely in their home to break up prolonged sitting time (e.g., stand up during TV commercials). The intervention should pose minimal risk of falling or injury since the participants will only be asked to engage in activities that are a part of their normal routine. There may be a risk of muscle soreness or increases in pain upon standing up and moving more. In addition, when completing the functional assessments (i.e., balance and chair stand tests), there may be risks of falling, muscle soreness, and pain. There also may be a risk to confidentiality, however, ID numbers will be used in place of participants' names on documents related to this study.

*Potential Benefits:* Older adults are the most sedentary age group spending 60-70% of their waking hours sitting. This amount of sitting time increases the risk of functional decline, chronic diseases, and premature mortality. The potential benefit of the proposed research to participants is acquiring knowledge on the negative health consequences of sedentary behavior (e.g., increased risk of obesity, metabolic syndrome, type 2 diabetes, cardiovascular disease, some malignancies, and premature death), and developing strategies to reduce sedentary behavior. Sitting less seems simple but intervention is required to get older adults to do it. If breaking up sitting time by standing up and moving more throughout the day proves to be effective, as our pilot data suggests, then we will have identified a practical intervention with the potential to improve the health and function of older adults.

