**Table 2. Schedule of Assessments**

Assessments	Introductory Meeting	Session 1	Session 2	Session 3	Session 4	Refresher Session 8 wks	Follow-up 12 wks
Informed Consent	X						
Demographic/health questionnaire	X						
SF-36	X				X		X
PROMIS questionnaires	X				X		X
Sedentary Behavior interview	X				X		X
Self-efficacy questionnaire	X				X		X
Self-regulation questionnaire	X				X		X
Outcome expectations questionnaire	X				X		X
Short Physical Performance Battery	X				X		X
Accelerometers	X				X		X
Adverse events			X	X	X	X	X
Fidelity monitoring		X	X	X	X	X	
Satisfaction						X	
Feasibility						X	
Cost estimate							X

Note. Screening of prospective participants and randomization will be completed prior to the introductory meeting.

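### Table 2 omits the adverse-event form at Session 1, contrary to the safety text; if the table is followed, the days after the baseline physical tests are not asked about

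*Combined protocol and SAP*

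**What the plan says.** The paragraph on adverse event collection and reporting (Safety, Participants Safety) tells the health program facilitators to "at the beginning of each workshop session, distribute a brief questionnaire asking about any adverse events" "that may have occurred during the previous week". It makes no exception for the first session. Session 1 is a workshop session both in the intervention description and in Table 1.

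Table 2 (Schedule of Assessments) has the row "Adverse events X X X X X". The five marks stand under Sessions 2, 3 and 4, the 8-week refresher and the 12-week follow-up. The cells for the introductory meeting and Session 1 are empty.

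Two other places bear on the gap. The Risks paragraph states that "when completing the functional assessments (i.e., balance and chair stand tests), there may be risks of falling, muscle soreness, and pain". The Measures paragraph dates the first of these tests: "Data collection sessions will be held the week prior to beginning the intervention (at the introductory meeting". Table 2 agrees, marking the Short Physical Performance Battery at the introductory meeting.

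**The concern.** A schedule of assessments is what site staff usually work from. Here it disagrees with the text on whether the first workshop session includes the adverse-event form.

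The missing form is the one that would look back over the week of the baseline balance and chair-stand tests. Those tests are a research procedure carried out after consent, and the plan itself lists their risks. If the table is used, a participant who became sore, had more pain or fell in the days after testing would not be asked about it on any scheduled form. What is at stake is the completeness of safety data for a named study procedure. No efficacy endpoint is touched.

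**Working it through.** The plan gives no figure to reproduce. The check sets the passages side by side and counts recall days.

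**1. Is the blank cell real?** The row "Fidelity monitoring X X X X X" has its marks at Sessions 1 to 4 and the refresher, so the Session 1 column is intact. The row "Short Physical Performance Battery X X X" has its marks at the introductory meeting, Session 4 and the 12-week follow-up, as the text requires. The columns are aligned, so the blank is not an artefact of reading the table.

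**2. Which forms does each source schedule?**

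| Occasion | Safety text | Table 2 |
|---|---|---|
| Session 1 | yes | no |
| Sessions 2, 3, 4 | yes | yes |
| Refresher, 8 weeks | yes | yes |
| Follow-up, 12 weeks | not mentioned | yes |
| Total | 5 | 5 |

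The totals agree, but only four occasions are shared. Session 1 appears only in the text and the 12-week form only in the table.

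**3. Which days do the forms reach?** Assumptions: Session 1 is day 0; Sessions 2 to 4 are days 7, 14 and 21; the refresher is day 56; follow-up is day 84; the introductory meeting falls between day −7 and day −1; each form recalls 7 days.

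- Span considered: 84 − (−7) = 91 days.
- Table 2 windows: 0–7, 7–14, 14–21, 49–56 and 77–84. Covered: 5 × 7 = 35 days.
- Not covered: −7 to 0 (7 days), 21 to 49 (28 days) and 56 to 77 (21 days). 7 + 28 + 21 = 56, and 35 + 56 = 91.
- With a Session 1 form added to Table 2: 6 × 7 = 42 days, now including days −7 to 0.

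The 35-day total is not itself the defect. Most uncovered days come from one-week recall combined with widely spaced later visits, and the text does not claim to cover those. The point is which week is lost: under Table 2 the earliest form, on day 7, looks back only to day 0, so the interval from the baseline tests to Session 1 lies outside every window.

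**4. What about the later tests?** The physical battery is repeated at Session 4 and at 12 weeks. After Session 4 the next form is the refresher, which looks back only to day 49. After the 12-week test no form follows. Restoring the Session 1 form therefore closes the baseline gap only.

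**The case against.** The best defence is that this is one empty cell, that the text is clear, and that a site following the text would ask about the baseline week. Session 1 also comes before any intervention exposure. The most serious acute event, a fall during testing, would happen beside an assessor positioned to help, at a meeting the principal investigator attends. Participants are also told what to report and to whom.

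Much of this stands. The gap exists only if Table 2 governs, and what it leaves unasked is mainly delayed. But the plan undertakes to document events during the study, and consent and testing take place at the introductory meeting. The self-reporting instruction is framed around events during the workshop, so it is not a solicited question about the tests.

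A reader might infer more, and the documents do not support it:

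- **That the baseline-test week is never asked about.** This is true only under Table 2.
- **That a Session 1 form would give a clean background rate, and that later reports mean little without it.** The preceding week contains the tests, so it is not free of exposure to study procedures. PROMIS pain measures and a health-history questionnaire are already completed at the introductory meeting, and the form asks about increases in pain. This is a partial baseline, since PROMIS pain does not cover falls, injury or soreness.
- **That arthritis will flood the forms with background reports.** The safety section says most pilot participants reported arthritis, but in the same note it reports no injuries and no increase in pain. The documents give no weekly background rate, and symptoms cluster within a person, so compounding an assumed rate over independent weeks would not be evidence about this trial.
- **That the monitoring board's summary would blame the programme for background symptoms.** The report is to describe events; nothing in the plan says it assigns cause.

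**Conclusion.** The contradiction is literal and the text and table must be reconciled. If Table 2 is the working schedule, up to 7 days per participant, from the baseline tests to Session 1, fall outside every adverse-event recall window. Delayed soreness, pain or falls after a procedure with acknowledged risks are then not solicited. This rests on the one-week recall stated in the text, weekly sessions, and a baseline meeting in the week before Session 1. It does not rest on any assumed event rate.

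This is an inconsistency in safety collection that is worth correcting before sites start because the correction costs almost nothing. It has no bearing on sample size, power or alpha.

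**What to change.** Add an adverse-event X under Session 1 in Table 2 so that it matches the safety text. Word that form to cover the period since the introductory meeting, so that it still reaches the tests if the meeting falls more than a week earlier. In the same edit, mention the 12-week form in the text, where it is now absent.

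The Session 1 form reaches the intervention arm only. Wait-list participants take the same baseline tests but attend no workshop until after week 12. Ask them the same question at whatever contact is used to recover the baseline activity monitors. The documents do not describe that contact, so it needs to be specified.

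Record all symptoms reported at later sessions. Report the Session 1 responses beside them as descriptive pre-intervention context. They should not serve as a background rate, nor as a filter on which later events count, since a filter could hide events.

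The cost is one table cell, one extra copy of a short existing form, and one question to controls.
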